8.5 Benefit-to Risk Rationale

The risks involved with the investigational devices to be evaluated under this clinical investigation are not substantially different from the risks associated with normal CI users, and the risks involved with the clinical investigation procedures are not substantially different from the risks associated with a normal clinical session for CI users.

The potential temporary inconveniences and discomforts associated with participation in this investigation is proportional to the indirect benefits, as described in section 8.1.

9 STATISTICAL CONSIDERATIONS

9.1 General Considerations

See sections 9.2 to 9.8 for statistical considerations.

9.2 Endpoints

For speech in quiet (CNC) endpoints, two lists of words will be measured per sound processor condition, and the two percentage words correct values will be averaged to produce a single value per condition, per subject.

For speech in noise (AuSTIN) endpoints, two lists of sentences will be measured per sound processor condition, and the two dB SRT values will be averaged to produce a single value per condition, per subject.

Each SSQ questionnaire which includes 12 questions will be measured per sound processor condition per person. The score is a continuous numeric score, and a single value will be recorded per question. For the SSQ12 endpoint, the total scores will be compared.

9.2.1 Primary Endpoints

- 1) Paired difference in percentage CNC Words correct between default and LP1 MAPs in quiet setting
- 2) Paired difference in dB SRT (AuSTIN) between default and LP1 MAPs in noise

9.2.2 Secondary Endpoints

- 1) Paired difference in percentage CNC Words correct between LP1 MAP and LP2 MAP in quiet setting
- 2) Paired difference in dB SRT (AuSTIN) between LP1 and LP2 MAPs in noise
- 3) Paired difference in percentage CNC Words correct between LP1 and LP3 MAPs in quiet setting
- 4) Paired difference in dB SRT (AuSTIN) between LP1 and LP3 MAPs in noise
- 5) Ratings on switching acceptability rating

9.2.3 Exploratory Endpoints

- 1) Paired difference in percentage CNC Words correct with LP2 and LP3 MAPs
- 2) Paired difference in dB SRT (AuSTIN) between LP2 and L3 MAPs
- 3) Paired difference in global SSQ12 scores after experience with LP1 and LP3 MAPs

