- Preparation of take-home sound processor: Group 1 will be provided with 900Hz MAPs (Default and LP1), and group 2 will be provided with 500Hz MAPs (LP2 and LP3) as per the randomisation table (Table 4). The SmartSound environments in the frequently used program in their own sound processor will be replicated in the study sound processor with the exception of automatic forward focus (SCAN2FF). Subjects using a SCAN2FF program in their own sound processor will be provided a SCAN2 program with user-controlled ForwardFocus enabled.
- Issue of SSQ12: The SSQ12 questionnaire will be issued, and the subjects will be counselled on how to
 complete the questionnaire as needed. The subjects will be asked to rate their ability to hear speech
 in a variety of competing contexts during their take home period. Subjects are also asked about their
 spatial hearing abilities including the impact of direction, distance and movement associated with
 spatial hearing.

CIP Number: CLTD5853

- Counselling for take home use: Subjects will be asked to switch from program 1 to program 2 on a daily basis so that they acclimate to both programs and to get equal opportunity to use both programs during the take home period. Subjects who typically used the SCAN2FF program prior to enrolment will be asked to use user-controlled ForwardFocus during the take home period.
- **Standard CRFs:** CRFs including concomitant medications, adverse events and device deficiencies will be completed.

Take home use:

- Subjects will be asked to use two MAPs for four weeks. The subjects will be asked to use P1 on day 1, P2 on day 2, P1 on day 3 etc.
- Subjects will be asked to complete the SSQ12 in the fourth week of take home use.

Visit 2:

- Collection of SSQ12:
- Acclimatization: Subjects will be asked to use the specified test MAP for a period of minimum 10 minutes and listen to live or recorded speech to acclimate to two conditions prior to speech perception testing. Contralateral device will be turned off (if applicable).
- **SAR:** The subjects will be asked to provide responses to the questions in the SAR as soon as they have switched to the new MAP at the end of the acclimatisation period.
- CNC word test (60dB): Two lists with 50 words each will be administered per condition. The
 contralateral ear will be plugged. The test order will be determined using the randomisation table (Table
 4)

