- AuSTIN sentence test: Both recorded speech and noise (adaptive four talker babble noise) will be presented from 0 degrees azimuth (S0N0). The signal level will be fixed at 65 dB SPL. One practice list will be administered at the beginning of the session to overcome learning effects. Two lists with 20 sentences each will be administered per condition. If the standard deviation (SD) for any list exceeds 4.12, then the run will be considered as invalid and additional list will be administered. The contralateral ear will be plugged.
- Loading MAPs to processors: CDI Tool will be used to load the test MAPs into a study sound processor for take home use as per the randomisation table (Table 4).
- **Issue of SSQ12:** The SSQ12 questionnaire will be issued, and the subjects will be counselled on how to complete the questionnaire as needed.
- **Standard CRFs:** CRFs including concomitant medications, adverse events, device deficiencies and device exposure will be completed.

CIP Number: CLTD5853

Take home use:

- Subjects will be asked to use two MAPs for four weeks. The subjects will be asked to use P1 on day 1,
 P2 on day 2, P1 on day 3 etc.
- Subjects will be asked to complete the SSQ12 in the fourth week of take home use.

Visit 3:

- Collection of SSQ12:
- Acclimatization: Subjects will be asked to use the specified test MAP for a period of minimum 10
 minutes and listen to live or recorded speech to acclimate to the two conditions prior to speech
 perception testing. Contralateral device will be turned off (if applicable).
- **SAR:** The subjects will be asked to provide responses to the questions in the SAR as soon as they have switched to the new MAP at the end of the acclimatisation period.
- **CNC word test (60dB):** Two lists with 50 words each will be administered per condition. The contralateral ear will be plugged. The test order will be determined using the randomisation table (Table 4)
- AuSTIN sentence test: Both recorded speech and noise (adaptive four talker babble noise) will be
 presented from 0 degrees azimuth (S0N0). The signal level will be fixed at 65 dB SPL. One practice list
 will be administered at the beginning of the session to overcome learning effects. Two lists with 20
 sentences each will be administered per condition. If the SD for any list exceeds 4.12, then the run will
 be considered as invalid and additional list will be administered. The contralateral ear will be plugged.

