7.4.3 Questionnaires

Paper-based questionnaires will be used to gather responses on SSQ12 from subjects and to be entered into EDC by site staff.

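### Is the SSQ12 comparison of LP1 with LP3 lost because the visit procedures do not say that each MAP is rated separately?

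*Combined protocol and SAP*

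**What the plan says.** Section 9.2 sets the unit of measurement for the questionnaire: "Each SSQ questionnaire which includes 12 questions will be measured per sound processor condition per person". It uses the same term, sound processor condition, for CNC words and AuSTIN, where a condition is a MAP. Section 9.2.3 then defines exploratory endpoint 3 as the "Paired difference in global SSQ12 scores after experience with LP1 and LP3 MAPs", and Table 3 in section 6 lists the same contrast.

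Section 7.3.2 describes the conduct. Each take-home period lasts four weeks and involves two MAPs: "The subjects will be asked to use P1 on day 1, P2 on day 2, P1 on day 3 etc". At Visits 1 and 2, "The SSQ12 questionnaire will be issued, and the subjects will be counselled on how to complete the questionnaire as needed". The Visit 1 text asks subjects to rate their hearing of speech "in a variety of competing contexts during their take home period". For completion, "Subjects will be asked to complete the SSQ12 in the fourth week of take home use". Section 7.4.3 adds the medium: "Paper-based questionnaires will be used to gather responses on SSQ12 from subjects". The schedule in section 3 marks SSQ12 at Visits 2 and 3.

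For the SAR, secondary endpoint 5 in section 9.2.2 and the summary in section 9.6.2 name no MAP pair. Objective 5 in section 6.2 and Table 3 name LP2 and LP3, and section 4.3 speaks of going from LP2 to LP3.

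**The concern.** Under Table 4, LP1 always shares its take-home period with the default MAP, and LP3 always shares its period with LP2. A questionnaire answered for the whole period would therefore describe a mixture of two MAPs. The speech-test steps in the same section are explicit about the unit; for CNC words, "Two lists with 50 words each will be administered per condition". The SSQ12 steps carry no such phrase, and the questionnaire appears in the singular. A site working only from the visit steps might issue one form per period.

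If so, exploratory endpoint 3 would have no usable data, and no later analysis could separate the MAPs. SSQ12 is also the one planned hearing-performance measure drawn from daily life; CNC, AuSTIN and the SAR are all done at the visit.

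The SAR raised a related worry. It is collected at both visits, and the test order in Table 4 runs in both directions. An undivided summary could therefore mix LP2-to-LP3 switches with LP3-to-LP2 switches, and possibly with default/LP1 switches.

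**Working it through.** The plan states no figure for SSQ12 or the SAR. Its only design figure is the power in section 9.4, which rests on CNC and AuSTIN. With a paired t-test, a true difference of 0, one-sided alpha 0.025 and n = 14, the noncentrality is margin / SD × √n:

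- AuSTIN: 1 / 1.037 × √14 = 3.61, power 0.915 (stated: 90%).
- CNC: 10 / 6.914 × √14 = 5.41, power 0.9987 (stated: more than 90%).

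The figure reproduces, and no SSQ12 or SAR quantity enters it.

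**1. Scores under each reading.** The inputs are four MAPs and two periods (Table 4), and 20 subjects enrolled with a minimum of 16 (section 9.4).

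| Reading | Per subject | 20 subjects | 16 subjects |
|---|---|---|---|
| One score per MAP (section 9.2) | 4 | 4 × 20 = 80 | 4 × 16 = 64 |
| One form per period (visit steps alone) | 2 | 2 × 20 = 40 | 2 × 16 = 32 |

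**2. What a blended form would estimate.** Assume, for illustration, that a period-level answer weights its two MAPs equally. The contrast between periods is then (LP2 + LP3)/2 − (default + LP1)/2. This is not LP3 − LP1, so the second reading cannot deliver the endpoint.

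**3. Which reading the plan supports.** Section 9.2 requires the first reading in terms. Section 9.2.3 and Table 3 need an LP1 score and an LP3 score from the same subject. Section 9.6.3 plans a plot of the average paired difference, which needs the same. Section 7.3.2 gives no number of forms; the singular can name the instrument as easily as a count. Nothing in it forbids separate ratings.

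**4. Whether separate ratings can be obtained under the design.** Table 4 gives these program positions:

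| Group | LP1 | LP3 |
|---|---|---|
| 1A | P2 | P2 |
| 1B | P1 | P1 |
| 2A | P2 | P2 |
| 2B | P1 | P1 |

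Subjects know their programs as P1 and P2, so they can rate each one without learning which MAP it holds. Within every subject, LP1 and LP3 occupy the same position, and Table 4 links position to MAP. Reading the visit steps together with section 9.2 therefore yields the endpoint in all four groups and keeps the subject blind.

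**5. SAR.** Assume one rating per visit, equal groups, and SAR order following the test order. At the LP2/LP3 visit, Groups 1A and 2A go from LP2 to LP3 (5 + 5 = 10 of 20, or 4 + 4 = 8 of 16). Groups 1B and 2B go the other way, in the same numbers. Objective 5 and Table 3 fix the pair, and the objective concerns switching between the two MAPs, which covers both directions. Section 9.6.3 lists SAR data and summarises them by treatment group. Whether that term means the MAP or the Table 4 group is not stated, but the listing with Table 4 recovers the direction either way.

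**The case for a change.** The strongest reply is that sites and subjects work from visit steps, not from a statistical section, and that the form is completed on paper away from the clinic. Counselling given as needed is not a written instruction to rate two programs. If one form per period were issued, the loss would be permanent, whereas a sentence in each of the two steps that issue the questionnaire would prevent it at little cost: at most two further 12-item forms per subject, or 24 items.

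Part of this stands. The visit text is less explicit for SSQ12 than for the speech tests, and the consequence of a single form is described correctly. It does not establish a defect in the plan. Protocol and statistical content are one document, carried out at one site that the sponsor runs with its own trained investigators (section 7.5). The loss requires that site to overlook a requirement in the document it works from. Nor can it be inferred from what is visible: the SSQ12 form is not among the appendices, Figure 4 is not shown, and the steps for collecting the questionnaire at Visits 2 and 3 have no text after their titles. Any of these might carry the instruction. The added sentences would repeat in one section what another already requires.

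**Conclusion.** The concern does not hold as a reason to change the plan. The intended data are one SSQ12 score per MAP per subject, stated in section 9.2 and presupposed by Table 3, section 9.2.3 and section 9.6.3. The visit steps leave out a detail that the site can supply from section 9.2 when it issues the form and counsels the subject. The difference between 40 and 80 scores arises only if a singular noun is read as a count and section 9.2 is set aside.

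The SAR point is a matter of reporting detail on an unvalidated, descriptive scale: the pair is fixed elsewhere in the plan, and the direction is recoverable from the listings.

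The stakes are limited in any case. SSQ12 is exploratory with no hypothesis (section 9.3.3), and SAR endpoint 5 also has none (section 9.3.2). The primary and secondary non-inferiority tests, their order and the power at n = 14 stay as they are. This conclusion assumes that condition in section 9.2 means a MAP for SSQ12, as it does for CNC and AuSTIN, and that the site reads the visit steps together with that section.

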9.3 Hypotheses

For the non-inferiority test of CNC words, the 95% CI (alpha=0.025 one-sided) for the mean paired difference will be estimated. If the lower limit of the 95% CI of the mean paired difference is above -10%, the treatment condition is regarded as non-inferior to the control on that measure.

For the non-inferiority test of SRT sentences for both primary and secondary endpoints, the 95% CI (alpha=0.025 one-sided) for the mean paired difference will be calculated. If the upper limit of the 95% CI of the mean paired difference is lower than 1dB, the treatment condition is regarded as non-inferior to the control on that measure.

9.3.1 Primary Hypotheses

Primary endpoint 1: Paired difference in percentage CNC Words correct between default and LP1 MAPs in quiet setting

H0: Words in quiet (60 dB CNC words) scores (% words correct) with the LP1 MAP are inferior to those with the default MAP.

H1: Words in quiet (60 dB CNC words) scores (% words correct) with the LP1 MAP are non-inferior to those with the default MAP.

Primary endpoint 2: Paired difference in dB SRT (AuSTIN) between default and LP1 MAPs in noise

HO: Sentence in noise scores (dB SRT) with the LP1 MAP are inferior to those with the default MAP.

LP1 MAP – default ≥ 1 dB (NB: higher SRT scores represent poorer performance)

H1: Sentence in noise scores (dB SRT) with the LP1 MAP are non-inferior to those with the default MAP

9.3.2 Secondary Hypotheses

Secondary endpoint 1: Paired difference in percentage CNC Words correct between LP1 MAP and LP2 MAP in quiet setting

H0: Words in quiet (60 dB CNC words) scores (% words correct) with the LP2 MAP are inferior to those with the LP1 MAP

H1: Words in quiet (60 dB CNC words) scores (% words correct) with the LP2 MAP are non-inferior to those with the LP1 MAP

CIP Number: CLTD5853

Secondary endpoint 2: Paired difference in dB SRT (AuSTIN) between LP1 and LP2 MAPs in noise

HO: Sentence in noise scores (dB SRT) with the LP2 MAP are inferior to those with the LP1 MAP

LP2 MAP – LP1 ≥ 1 dB (NB: higher SRT scores represent poorer performance)

H1: Sentence in noise scores (dB SRT) with the LP2 MAP are non-inferior to those with the LP1 MAP

LP2 MAP - LP1 < 1 dB

Secondary endpoint 3: Paired difference in percentage CNC Words correct between LP1 and LP3 MAPs in quiet setting

H0: Words in quiet (60 dB CNC words) scores (% words correct) with the LP3 MAP are inferior to those with the LP1 MAP

LP3 - LP1 < -10%

H1: Words in quiet (60 dB CNC words) scores (% words correct) with the LP3 MAP are non-inferior to those with the LP1 MAP

LP3 - LP1 > -10%

Secondary endpoint 4: Paired difference in dB SRT (AuSTIN) between LP1 and LP3 MAPs in noise

H0: Sentence in noise scores (dB SRT) with the LP3 MAP are inferior to those with the LP1 MAP LP3 MAP − LP1 ≥ 1 dB (NB: higher SRT scores represent poorer performance)

H1: Sentence in noise scores (dB SRT) with the LP3 MAP are non-inferior to those with the LP1 MAP LP3 MAP - LP1 < 1 dB

Secondary endpoint 5: Ratings on switching acceptability rating.

There are no hypotheses for this endpoint.

9.3.3 Exploratory Hypothesis

There are no exploratory hypotheses.

9.4 Sample Size Determination

This study is a non-inferiority design, and sample size calculation was based on non-inferiority tests for CNC word scores and SRT (Speech Recognition Threshold) scores.

To reject the null hypothesis of inferior CNC Words correct in quiet (60 dB) scores, a sample size of 14 will provide more than 90% power to detect non-inferiority of CNC word scores and 90% power to detect non-inferiority of SRT with the following parameters:

CIP Number: CLTD5853

- A clinically important difference value of 10% for CNC words and 1 dB SRT for AuSTIN. This margin is based on clinical consensus.
- A SD of change or difference scores of 6.914% for CNC words and 1.037 dB for AuSTIN. The expected standard deviation of difference scores for CNC words was based on a previous dual electrode mode study (CRC 5523) on the relevant endpoints.
- A significance level $\alpha = 0.025$ (one-tailed).

There are four subgroups in the randomisation table (Table 4); to ensure equal number of subjects in each subgroup a minimum of sample size of 16 (or a higher multiple of 4) is required. Twenty subjects will be enrolled in total to allow for any unforeseen subject withdrawal with a possible attrition rate of 25% and to ensure equal number of subjects in the four subgroups. Replaced subjects will be recruited if the minimum sample size of 16 could not be met due to subject withdrawal or loss to follow up.

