7.2.3 Number of Subjects Required

Twenty subjects will be enrolled in the study to meet sample size calculation requirements stated in section 9.4 with the allowance for dropout rate (25%) and to ensure balanced subgroups.

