7.2.5 Recruitment and Study Duration

The following subject status definitions apply:

- Enrolled: A subject that has signed the Informed Consent form for the study.
- Screen Fail: An Enrolled subject that has been determined to not meet one or more eligibility criteria.
- Participated: Subjects who have met eligibility criteria and have commenced visit 1 procedures.
- Discontinued: An Enrolled subject who withdrew consent, was discontinued by the Investigator or Sponsor before the expected End of Study visit or lost to follow-up. Discontinued subjects may still have safety follow up data collection until their scheduled End of Study visit, for reasons described in section 7.2.6.
- Completed: Enrolled subjects who complete the required treatment and visit schedule.

The recruitment period for the clinical investigation is estimated to be seven months from the time of first subject consent to recruitment of the last subject. This is to allow the replacement of any subjects who withdraw from the study.

The expected minimum duration of each subject's participation in the clinical investigation, is eight weeks, from the time of informed consent through to the End of Study when devices are returned. The anticipated total duration of the clinical investigation is 12 months.

CIP Number: CLTD5853

Clinical Investigation completion is last subject last visit. In the event of an ongoing SAEs/SADEs at the time of this last visit, the clinical investigation completion will be extended for a further 30 days, or until resolution or stabilisation of the event, whichever comes first.

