7.2.6 Criteria and Procedures for Subject Withdrawal

Subjects can decide to withdraw from the investigation at any time. The Investigator shall ask the reason(s), however subjects have the right to withhold their reason if preferred. The reason for withdrawal should be documented in the subject's source files and the case report form (CRF), if provided.

The Investigator or Sponsor may also decide to withdraw a subject from the clinical investigation or stop the use of the investigational device if it is considered to be in the subject's best interests.

Subject withdrawal may be for any of the following reasons:

- Adverse Event (AE)
- Device Deficiency (DD)
- CIP or GCP deviation
- Subject withdrew consent
- Subject lost to follow-up
- Subject death
- Sponsor decision
- Investigator decision
- Other (specify)

If subject withdrawal is due to problems related to the IMD safety or performance, the Investigator shall ask for the subject's permission to continue in safety follow up (for example, adverse events and device deficiencies) until their scheduled End-of-Study visit.

If a subject is lost to follow-up, every possible effort must be made by the study site personnel to contact the subject and determine the reason for discontinuation. At least 3 separate attempts taken to contact the subject must be documented.

Participating subjects who are withdrawn/discontinued before the data for primary and secondary endpoints have been collected, may be replaced to meet the minimum sample size criteria or to maintain counterbalancing between the groups.

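### Does the 25% attrition allowance fail because 20 enrolled subjects would leave 15, one below the minimum of 16?

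*Combined protocol and SAP*

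**What the plan says.** Section 9.4 builds the sample size in four steps.

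- **Power:** "a sample size of 14 will provide more than 90% power to detect non-inferiority of CNC word scores", and 90% power for the sentence test in noise (SRT).
- **Balance:** because Table 4 has four subgroups, "a minimum of sample size of 16 (or a higher multiple of 4) is required".
- **Attrition:** "Twenty subjects will be enrolled in total to allow for any unforeseen subject withdrawal with a possible attrition rate of 25"%, with equal subgroups given as a second reason for choosing 20.
- **Replacement:** "Replaced subjects will be recruited if the minimum sample size of 16 could not be met due to subject withdrawal" or loss to follow-up.

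Three other sections bear on the point. Section 7.2.3 says that 20 subjects meet the requirements of the calculation in 9.4, "with the allowance for dropout rate (25%) and to ensure balanced subgroups". Section 7.2.6 says that participants who leave before their primary and secondary endpoint data are collected "may be replaced to meet the minimum sample size criteria or to maintain counterbalancing between the groups". Section 7.2.5 explains the length of the seven-month recruitment period: "This is to allow the replacement of any subjects who withdraw from the study".

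**The concern.** The attrition sentence in 9.4 comes directly after the minimum of 16 and directly before a replacement rule triggered by 16. Read in that order, 16 is the number to be kept after withdrawals, and 20 subjects are said to protect it against 25% attrition. They do not: 15 would remain, and 15 cannot be divided equally among four subgroups. The figure 20 is also 16 x 1.25, which suggests the common slip of adding 25% when the calculation should divide by 0.75.

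If that were what happened, the plan would state a tolerance it does not have. A trial losing subjects at its own planning rate would fall below its own minimum, and a reader could fairly ask whether power or the counterbalancing of test order was at risk.

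**Working it through.** **Inputs.** From 9.4: powered n = 14; minimum for balance = 16; enrolled = 20; attrition 25%; margins 10 percentage points (CNC words) and 1 dB (SRT); SDs of paired differences 6.914 percentage points and 1.037 dB. From 9.3: "the 95% CI (alpha=0.025 one-sided) for the mean paired difference will be estimated". The documents state no true difference; zero is assumed first, and a range follows.

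**1. Reproduce the 14.** Power of the paired non-inferiority t-test is P(T > t(0.975, n-1)), where T is noncentral t with n-1 degrees of freedom and noncentrality (margin/SD) x √n. For SRT at n = 14 the noncentrality is (1/1.037) x √14 = 3.61; for CNC words it is (10/6.914) x √14 = 5.41.

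| n | SRT power | CNC power |
|---|---|---|
| 13 | 89.0% | 99.75% |
| 14 | 91.5% | 99.87% |
| 15 | 93.4% | 99.94% |
| 16 | 95.0% | 99.97% |

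Fourteen is the smallest n with at least 90% power on SRT, so the plan's figure reproduces with a true difference of zero.

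**2. Attrition against each candidate base.**

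| Base | Enrolment needed at 25% loss | Next multiple of 4 | Losses that 20 can absorb |
|---|---|---|---|
| 14 (power) | 14/0.75 = 18.7, so 19 | 20 | 6 of 20 = 30% |
| 16 (balance) | 16/0.75 = 21.3, so 22 | 24 | 4 of 20 = 20% |

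On a base of 14, the planned 20 comes out exactly, and 25% lies within the 30% that 20 subjects can absorb. On a base of 16 it comes out only by the slip 16 x 1.25 = 20.

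**3. Which base do the documents support?** Section 7.2.3 gives the reasons for 20 in order: the sample size calculation, the dropout allowance, balanced subgroups. Taken in that order, they are 14, then 19, then 20. The attrition sentence in 9.4 has the same structure, with equal subgroups named as a further reason after the attrition rate. The documents do not state the route outright, but one route involves no error and yields the planned number.

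**4. What happens at 25% attrition.** 20 x 0.75 = 15 remain. Fifteen exceeds 14, and falling below 16 triggers the replacement rule in 9.4: 16 - 15 = 1 replacement.

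**5. Cost if that replacement were never found (15 analysed in place of 16), SRT.**

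| True deficit of LP1 | n = 15 | n = 16 | Loss in power |
|---|---|---|---|
| 0 dB | 93.4% | 95.0% | 1.5 points |
| 0.1 dB | 87.8% | 90.0% | 2.2 points |
| 0.2 dB | 79.3% | 82.2% | 2.9 points |
| 0.3 dB | 68.2% | 71.4% | 3.2 points |

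Losses are taken from unrounded values. For true CNC deficits of 0 to 3 percentage points the loss is at most 1.2 points (95.4% against 96.6% at a deficit of 3).

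**The case for a change.** The strongest case for a correction is that 16 is plainly a number to be held after withdrawals, since 9.4 triggers replacement on it, and an attrition allowance ought to protect the number that has to be held. Replacement is a separate provision: if 20 truly covered 25% against 16, it would not be needed at 25%. Nor would it be a rare fallback. If each of 20 subjects withdrew independently with probability 25%, five or more would leave with probability 58.5%, and the count would fall below 16. Seven or more would leave, taking the count below 14, with probability 21.4%. One sentence would remove the doubt.

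The arithmetic stands, and so does the observation that 9.4 does not name the base of its 25%. The inference that the figure is wrong does not. The plan nowhere claims that 20 subjects keep 16 at 25% loss without replacement; its next sentence provides for exactly that shortfall, and 7.2.5 allows recruitment time for it. The binomial figures describe how often the rule would be used, not a failure of it. Divisibility of 15 by four adds little, because 16 remaining subjects need not be balanced either: four withdrawals can all fall in one subgroup. Balance after dropout rests on replacement under 7.2.6, not on what 20 x 0.75 happens to be.

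Replacing 25% by 20% in 7.2.3 would be a step backwards. The 25% is an assumed withdrawal rate; the 20% is what 20 subjects can absorb against 16. One is not a correction of the other.

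**Conclusion.** No change follows. The allowance is consistent with the plan's own calculation when it is read against the powered number of 14, and 7.2.3 supports that reading. Read against 16, it is short by one subject at 25% attrition, and the replacement rule in 9.4 makes up that subject. Power at 15 is still above the 90% target under the planning assumptions, and the planned analysis (section 9.6.1), a confidence interval for a mean paired difference, does not require equal subgroups.

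What is left is a detail of wording: 9.4 does not say which number the 25% protects. Naming it would leave the planned 20, the power, the analysis and every conclusion as they are.

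This rests on two conditions. The replacement rule in 9.4 must be applied as an obligation (7.2.6 words replacement as permissive). The power figures take the SDs in 9.4 and a true difference of zero; a real deficit would lower power at 14, 15 and 16 alike, which is a question about the planning assumption and not about attrition.
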